The proposed pilot study aims to directly compare conventional angiography imaging to ICG microangiography in adult patients with severe frostbite. Severe frostbite is defined as 4th degree: frostbite resulting in vascular occlusion and tissue ischemia. Both imaging modalities have been used for the diagnosis and monitoring of severe frostbite injury but there has never been a study directly comparing these two imaging modalities^{2,7-8}. We will be obtaining consent from adult patients with severe frostbite injury who are undergoing intra-arterial thrombolysis. During their treatment, an angiography will be performed according to the Regions Hospital standard of care protocol, followed immediately by an ICG microangiography image. These two diagnostic images will be directly compared by a radiologist and a burn surgeon to determine the image concordance or discordance. We will also monitor patients for potential side effects or adverse reactions to the ICG imaging, but as stated above, the ICG microangiography is low-risk and we do not anticipate any adverse reactions related to this procedure.

Pending the results of this study, we will pursue a full-scale version of this study, which will track patients in a longitudinal manner to determine the outcome of their frostbite treatments. The proposed pilot study is designed to assess feasibility, the degree of concordance or discordance between the two imaging modalities, and side effects of imaging.

2. Study Aims

Primary Outcome: Angiography and ICG microangiography imaging concordance/discordance.

Research question: Does the vascular cut off on conventional angiography found in severe frostbite patients correlate with the tissue ischemia demonstrated on ICG microangiography in severe frostbite?

Hypothesis: Conventional angiography can fully delineate the vascular occlusion (cut off) found in severe frostbite patients in highly granular detail. ICG microangiography shows the microvascular soft tissue perfusion and demonstrates where the tissue is ischemic in severe frostbite injury. We hypothesize that these two imaging modalities will be concordant at demonstrating the ischemic tissue present in severe frostbite.

Secondary Outcome: Safety.

Research question: Is indocyanine green safe when delivered in close association with contrast dye (used in conventional angiography)?

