scans, SPECT imaging, and indocyanine green (ICG) microangiography¹⁶. All of these imaging modalities demonstrate the perfusion of the affected tissue but do not allow for directed delivery of thrombolytics. In institutions that use these imaging techniques, thrombolytics are typically delivered in an intravenous fashion rather than intra-arterial.

ICG microangiography is a technology that has had rapidly expanding applications in recent decades. These have included retinal imaging, determining perfusion of colorectal anastomoses, biliary imaging, and assessing the blood supply of tissue flaps¹⁷⁻¹⁹. It has recently been used in diagnosis of frostbite with good correlation with severe final amputation levels. It is easy to use, non-radiating, can be performed at the bedside, and cheaper than other imaging modalities⁷⁻⁸.

Given that every hospital has different diagnostic and treatment algorithms, these different imaging modalities have rarely been compared in the same patient. The current best metric is comparing the imaging modality with the amount of tissue that is amputated as demonstrated in prior studies cited here. This research application provides a unique opportunity to compare two imaging modalities head-to-head in the same patient and determine their concordance or discordance.

4. Study Design

This pilot study is an unblinded prospective interventional imaging study designed to determine whether ICG microangiography is as accurate as conventional angiography in determining the ischemic tissue present in severe frostbite.

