2. Feasibility: Based on historical data from Regions Hospital between 2006-present, there are typically 20-70 patients per winter who undergo conventional angiography and catheter directed lytics who would be candidates to participate in this study. We anticipate approaching 20 patients to reach our target sample size of 10.

Data collection process

1. Process for identification of patients: All patients undergoing catheter directed thrombolysis for severe frostbite injury are managed primarily by the Burn Team. As such, the burn surgeons and burn advance practice practitioners will be able to identify patients who meet the inclusion criteria for this study.
2. Recruitment: The burn surgeon will identify patients and confirm that they meet the inclusion/exclusion criteria for the study. They will inform the Clinical Research Coordinator from the Critical Care Research Center (CCRC), who will approach the patient about the study and obtain informed consent.
3. Consent: Written consent will be obtained by the CCRC Clinical Research Coordinator who is the Lead Coordinator for this study (see attached ICF). Competency to provide consent will be confirmed by the coordinator obtaining consent by testing for comprehension after the consent conversation and before a signature is obtained.

Data sources

Data sources will include chart review, conventional angiography images, and ICG microangiography images. Images and data will be stored on an encrypted HealthPartners computer at Regions Hospital.

Data acquisition

- Data will be collected by [name], burn surgeon.
- Patient contact by study personnel will include consenting the patient for this study (CCRC Clinical Research Coordinator) and performance of the ICG microangiography study (performed by [name]).
- Data points from the Electronic Medical Records will include:
 - MRNs
 - Last name, first name
 - Basic demographics: age, gender, race, ethnicity
 - Social: substance abuse, mental health diagnoses, housing status
 - Medical: comorbid conditions CAD/vascular disease, diabetes mellitus, renal insufficiency, smoking
- Data from the conventional angiography include:
 - Medications currently being infused
 - Hours of treatment
 - Areas of poor perfusion as measured by the Hennepin Frostbite Score ²⁰ (see attached score sheet)
- Data from the ICG microangiography include:
 - Areas of poor perfusion as measured by the Hennepin Frostbite Score

DATA DICTIONARY GOES HERE

Statistical Analysis Plan

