The primary dependent variable in this study is the Hennepin Frostbite Score that will be generated from each imaging technique. We will compute a correlation between the Hennepin Frostbite Score produced by the conventional angiography and the Hennepin Frostbite Score produced by the ICG microangiography. While we predict a high correlation between the scores generated by the two methods, a high correlation does not necessarily imply that there is good agreement between the two methods. Thus, we will also use a Bland-Altman (difference) plot to analyze the agreement between the two imaging techniques.

Power analysis or statement of precision

This will be a small pilot study that will not be adequately powered to determine significance.

5. Interventions and treatments

As previously stated, the main intervention in this study is the performance of an ICG microangiography study immediately following a conventional angiography image in patients who are undergoing catheter directed thrombolysis for severe frostbite injury. This will be a one-time diagnostic measure with no additional follow up or imaging required. This is not a therapeutic intervention, but a secondary imaging study with minimal risk.

6. Setting/Environment/Organizational feasibility

Study participants will be patients who are being treated primarily on the Burn Unit at Regions Hospital. Consent will be obtained while they are inpatient by a CCRC Clinical Research Coordinator. The ICG microangiography imaging will be performed in the Interventional Radiology (IR) suite immediately following the patient's conventional angiography imaging. This has been discussed with the IR leadership and they agree to performing this study in their space (see attached Letter of Support). [name], burn surgeon, will be performing the ICG microangiography and staying in constant communication with the IR staff performing the conventional angiography imaging. Given the small number of images need for this pilot study, this method of communication and number of ICG providers will be adequate.

7. Risks and Benefits

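### The SAP analyses only Hennepin scores: if these are patient totals it tests agreement in extent, not location, and the planned two-reader concordance reading has no rule, data item or analysis

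*Combined protocol and SAP*

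**What the plan says.** The outcome and the analysis are described in different places and in different terms.

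- Section 2 (Study Aims) sets "Primary Outcome: Angiography and ICG microangiography imaging concordance/discordance". Its research question is "Does the vascular cut off on conventional angiography found in severe frostbite patients correlate with the tissue ischemia demonstrated on ICG microangiography", and its hypothesis paragraph says that ICG "demonstrates where the tissue is ischemic in severe frostbite injury".
- Section 1 (Summary) says how the outcome will be determined: "These two diagnostic images will be directly compared by a radiologist and a burn surgeon to determine the image concordance or discordance". It lists "the degree of concordance or discordance between the two imaging modalities" among the things the pilot is designed to assess, and a full-scale study depends on the results.
- Section 4 (Study Design) describes the study as "designed to determine whether ICG microangiography is as accurate as conventional angiography in determining the ischemic tissue present in severe frostbite".
- Data acquisition lists, for each modality, "Areas of poor perfusion as measured by the Hennepin Frostbite Score". It refers to an attached score sheet that is not in the text available. The data dictionary is an unfilled placeholder.
- The Statistical Analysis Plan makes the Hennepin score from each technique the primary dependent variable: "We will compute a correlation between the Hennepin Frostbite Score produced by the conventional angiography" and the ICG score. It notes, rightly, that a high correlation is not agreement, and adds a Bland-Altman plot. Nothing else is planned.

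**The concern.** The aims ask whether the two images identify the same ischemic tissue. A single score per patient and modality cannot answer that. It reduces each image to an amount, and two images can show the same amount in different places. Correlation and Bland-Altman analysis both take those amounts as input, so adding the second does not recover the location.

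The direct comparison by two readers is the one planned step that could. However, the documents do not define concordant, do not say whether the readers work independently or how they settle a disagreement, list no concordance call among the data to be collected, and give no analysis of one.

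At stake is the pilot's main product. Followed as written, the plan could report agreement on how much tissue is ischemic as if it were agreement on which tissue is ischemic, and a full-scale study would be built on that. A concordance rule devised after the images have been seen, in an unblinded study, would carry less weight.

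**Working it through.** **The plan's own figures.** There is no agreement figure to reproduce. The sample size is 10 patients, with one ICG image each. No power or precision calculation is given, and adequate power is disclaimed.

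**Limiting case.** Inputs: 10 patients (Sample size section); 20 scorable digits and 1, 2, …, 10 affected digits across patients (assumptions). Let both images show the same number of affected digits in each patient, but on entirely different digits.

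- Every difference in totals is 0, so r = 1.00, bias = 0 and the limits of agreement are 0 to 0.
- Each modality marks 1 + 2 + … + 10 = 55 digits, with none in common. Positive agreement = 2 × both / (angiography + ICG) = 2 × 0 / (55 + 55) = 0.
- Of 200 digits, 110 are discordant, so raw agreement is 90/200 = 0.45. Chance agreement is 0.275² + 0.725² = 0.601. Kappa = (0.45 − 0.601) / (1 − 0.601) = −0.38.

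Both planned analyses are perfect while agreement in location is nil.

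**Less extreme cases.** Assumptions: 10 patients, 20 digits, affected count uniform on 1 to 12, score = number of affected digits. ICG misses each affected digit with probability q. A share s of misses is offset by an over-call on an unaffected digit in the same patient. The remaining over-calls are independent, with mean (1 − s) × q × affected count, so that average over-calls equal average misses. Each setting was simulated 4,000 times; the figures are medians.

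| q | s | q(1 − s) | r | Limits of agreement, ± digits | Positive agreement |
|---|---|---|---|---|---|
| 0.1 | 0 | 0.10 | 0.96 | 2.02 | 0.90 |
| 0.2 | 0.50 | 0.10 | 0.96 | 2.02 | 0.80 |
| 0.3 | 0.65 | 0.105 | 0.96 | 2.02 | 0.70 |
| 0.2 | 0 | 0.20 | 0.93 | 2.74 | 0.80 |
| 0.3 | 0 | 0.30 | 0.91 | 3.13 | 0.69 |

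Bias is 0 throughout. Repeat runs gave limits that differed by less than 0.1 digit and positive agreement within 0.01.

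The first three rows coincide for a simple reason. A miss that is offset leaves the total unchanged, so the difference in totals depends essentially on the misses that are not offset, at rate q(1 − s). That rate is 0.1 × 1 = 0.10, 0.2 × 0.5 = 0.10 and 0.3 × 0.35 = 0.105. Agreement in location depends mainly on q itself and is close to 1 − q. With full offsetting (s = 1), r = 1.00 and the limits are 0 by construction, while positive agreement is 0.91, 0.81 and 0.70 for q = 0.1, 0.2 and 0.3.

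The last two rows show the other side: when errors do not offset, the limits widen with the error rate, so the Bland-Altman plot reveals part of the problem.

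**Precision of the proposed measure.** Half-width of the 95% interval for the mean of 10 patient values = t(0.975, 9 df) × SD / √10. In the illustration the between-patient SD runs from 0.09 to 0.21. This gives 2.262 × 0.09 / 3.162 = 0.06, and 2.262 × 0.21 / 3.162 = 0.15.

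**The case against.** *The score sheet is not visible.* If scores are recorded and paired by limb or digit, offsetting across areas largely disappears. This stands as a condition on the location point. It does not remove the concern: the SAP does not state the unit of the score, refers to it as one score from each technique, and plans no area-matched analysis even if areas are recorded.

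*The location aim is partly inferred.* The phrase about where tissue is ischemic describes what ICG does, and the research question asks whether the findings correlate, which the SAP answers literally. But the primary outcome is concordance, and the Study Design section asks about accuracy in determining the ischemic tissue. Equal amounts in different places would satisfy neither.

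*The Hennepin comparison may be how the readers' judgement is put into numbers.* That is possible, but the documents never make the link. On that reading the concordance rule and the assignment of readers to scores are still missing.

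*The illustration is constructed.* It is: the offset shares were set so that the score-based results coincide, and nothing in the documents supports 50% or 65% offsetting. If ICG only missed digits, at 30% with a mean of 6.5 affected, the bias would be 0.30 × 6.5 = 1.95 digits too few, and Bland-Altman would show it. The illustration establishes possibility, not likely size.

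*It is a 10-patient pilot, and the stored images could be read again later.* Both are true. But measuring concordance is a stated purpose of the pilot, and a rule written after the fact is weaker.

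**Conclusion.** The concern holds, and the plan should be changed. Two parts differ in certainty.

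The absence of a rule, data item and analysis for the two-reader concordance reading follows from the text available, whatever the form of the score. The blindness to location is conditional on the analysed scores being patient totals. Under that condition it follows from arithmetic: identical totals give perfect planned statistics whether or not any area matches.

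How large the discrepancy would be in practice cannot be known from the documents, which give neither an error rate nor an offset share. Under the stated assumptions, results that look the same on the planned statistics (r 0.96, bias 0, limits about ±2.0 digits) are compatible with positive agreement anywhere from 0.90 down to 0.70. The plan deserves credit for not relying on correlation alone. The gap lies in how the primary outcome is defined and captured, not in the sample size.

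**What to change.** State whether the Hennepin score is analysed as a patient total or by area, and make location-matched agreement the primary analysis:

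1. Record poor perfusion by area (limb or digit, as the score sheet allows) for each modality, and fill in the data dictionary accordingly.
2. Before any image is read, write the concordance rule for the two readers already planned. Each area is ischemic on both images, on angiography only, on ICG only, or on neither. Where it is ischemic on both, note whether the level of cut-off is the same or differs, and in which direction. State whether the readers work independently and how disagreement is settled.
3. For each patient compute positive agreement = 2 × (areas ischemic on both) / (areas ischemic on angiography + areas ischemic on ICG), over areas assessed by both modalities.
4. Report each patient's value and the mean with a 95% interval, with the patient as the unit. List discordant areas by direction, and tabulate differences in cut-off level among areas ischemic on both. Count patients with no deficit on either image separately, because the index is undefined for them.
5. Keep the score correlation and the Bland-Altman plot as supporting analyses of extent.

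The cost is SAP wording, a written rule, area-level data entry and a small extra analysis. No new imaging, readers or patients are needed. If the score sheet does not record by area, the stored images would have to be read by area. With 10 patients the interval on mean positive agreement would be about ±0.06 to ±0.15 under the illustration's spread, so it should be presented as an estimate for planning.

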We will capture images of 10 patients who are undergoing conventional angiography and thrombolysis for severe frostbite. All patients will be adults (>18 years old) and able to provide consent for participation in the study. Once the patient has been started on thrombolysis, they will be evaluated for whether they meet the study's inclusion/exclusion criteria, and then approached by a CCRC Clinical Research Coordinator about possible involvement in this research project. If they consent to the study, then the ICG microangiography imaging will be performed immediately following their next conventional angiography session. When a patient is undergoing catheter directed thrombolysis, they have conventional angiography sessions to assess progression every 24 hours for up to 72 hours. In this pilot study, we would administer the ICG microangiography following one of these sessions, after consent is obtained. This imaging would be performed in the IR suite immediately following the conventional angiography session.

This study is quasi-experimental. The inclusion of a second (ICG) imaging technique is not a therapeutic modality and has limited risks to the study participants. ICG dye is very well tolerated and only contraindicated in iodine allergy. There is no radiation associated with this imaging study. Participants will serve as their own controls as they will be receiving both types of imaging.

Population

Patients will be identified by the burn surgeons and advance practice practitioners. They will evaluate the patients to determine whether they meet the inclusion/exclusion criteria of the study.

a. Inclusion criteria

1. Adult (>18 years old) patients
2. Diagnosed with severe frostbite by conventional angiography
3. Undergoing thrombolysis with catheter directed lytics
4. Clinically sober at the time of consent
5. Cognitively able to provide consent as determined by clinician's best judgement
6. Normal kidney function (GFR >60)

b. Exclusion criteria

1. Pregnant. Pregnancy will be determined by standard of care pregnancy test performed on all female frostbite patients who are receiving lytics.
2. Iodine allergy.

c. Sample size

1. Ten ICG images will be performed on 10 unique patients who are already receiving conventional angiography as standard of care.

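### The SAP does not define its Bland-Altman limits; with 10 pairs, the conventional ±1.96 SD would cover on average about 91% of future differences, not 95%

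*Combined protocol and SAP*

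**What the plan says.** The Statistical Analysis Plan in Section 4 sets the outcome: "The primary dependent variable in this study is the Hennepin Frostbite Score that will be generated from each imaging technique". It plans a correlation between the two sets of scores, concedes that a high correlation would not establish agreement, and adds that "we will also use a Bland-Altman (difference) plot to analyze the agreement between the two imaging techniques".

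The number of pairs is fixed under Sample size in the same section: "Ten ICG images will be performed on 10 unique patients who are already receiving conventional angiography as standard of care". Section 5 confirms a single ICG study per patient: "This will be a one-time diagnostic measure with no additional follow up or imaging required". There are thus 10 independent differences and no replicates.

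Under the heading for power or precision, the plan says only "This will be a small pilot study that will not be adequately powered to determine significance". It does not say how limits of agreement will be calculated, what share of patients they are meant to contain, whether they will carry confidence intervals, or what size of difference would count as agreement.

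**The concern.** Because the SAP itself discounts the correlation, the Bland-Altman plot is its statistical analysis of agreement. The usual default for that plot, mean difference ± 1.96 SD, treats the mean and SD of the differences as known. With 10 pairs both are estimated, and limits that ignore this are on average too narrow to hold 95% of new patients' differences.

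The error has a direction: narrow limits make the two techniques look more interchangeable, which is what Section 2 hypothesises. The result is also meant to be used. Section 1 makes a full-scale study depend on it, Section 8 suggests it may bear on the choice of reference standard for frostbite imaging, and Section 11 plans publication. If the limits were presented as 95% limits, the reported degree of concordance would be somewhat too favourable in each of these uses.

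**Working it through.** The plan states no limit, SD, margin or coverage, so there is no figure of its own to reproduce.

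**Inputs**
- n = 10 pairs, one per patient (Section 4, Sample size; Section 5).
- Method: Bland-Altman difference plot (Section 4, Statistical Analysis Plan).
- Assumed, not in the documents: limits at mean ± 1.96 SD (2.0 as a variant), SD with divisor n − 1, target coverage 95%, roughly normal differences.

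**1. Expected coverage of a new patient's difference**

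A new difference minus the sample mean has variance σ²(1 + 1/n), so mean ± m × SD has expected coverage 2 × F(m / √(1 + 1/n)) − 1, where F is the t distribution function with n − 1 degrees of freedom.

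- m = 1.96: 1.96 / √1.1 = 1.96 / 1.0488 = 1.869, and with 9 degrees of freedom the coverage is **90.6%**. About 1 patient in 11 falls outside, instead of 1 in 20.
- m = 2.0: 91.1%.

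**2. Variation between studies**

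In 1,000,000 simulated samples of 10 normal differences, mean coverage of the 1.96 SD limits was 90.5% and the median was 92.9%. Coverage was below 95% in 63% of samples and below 90% in 36%; the 5th percentile was 74%.

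**3. Multiplier for 95% expected coverage**

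t(9; 0.975) × √1.1 = 2.262 × 1.0488 = **2.37**. Relative width: 2.3726 / 1.96 = 1.21, or 21% wider. Simulated mean coverage with this multiplier was 95.0%, but 33% of samples still covered less than 95%.

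**4. Precision of each conventional limit**

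Standard error in SD units: √(1/10 + 1.96² / (2 × 9)) = √(0.1000 + 0.2134) = 0.560. The 95% half-width is 2.262 × 0.560 = **1.27 SD**. That is about three times the shift from 1.96 to 2.37, which is 0.41 SD.

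**5. Sensitivity**

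| Situation | Coverage, ±1.96 SD | Coverage, t-based multiplier |
|---|---|---|
| n = 9, normal | 90.0% | 95% (multiplier 2.43) |
| n = 8, normal | 89.3% | 95% (multiplier 2.51) |
| n = 100, normal | 94.6% | 95% (multiplier 1.99) |
| n = 10, rounded to whole numbers, SD 2 | 90.6% | 95.0% |
| n = 10, rounded to whole numbers, SD 1 | 91.1% | 94.5% |
| n = 10, heavy tails (t with 3 df) | 89.4% | 92.9% |
| n = 10, skewed (exponential) | 90.9% | 93.1% |
| n = 10, half of the differences zero | 87.4% | 90.8% |

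The shortfall comes from the small n and almost disappears by n = 100. The t-based multiplier restores less when the differences are far from normal.

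**The case against.** The strongest objection is that the plan contains no wrong number. A reader might infer that the SAP commits to ±1.96 SD and labels it 95%. It does neither, so this is an unspecified calculation whose usual default under-covers, not an error in a stated figure. That stands.

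Second, the 21% depends on reading the limits as a prediction interval for a new patient. If they are instead estimates of the population 2.5th and 97.5th percentiles, the only systematic shortfall is the small-sample bias of the SD (expected SD about 0.973σ at n = 10, or about 2.7% too narrow), and confidence intervals are the natural way to show the uncertainty. This also stands. It is why the limits need a stated target, and why confidence intervals belong beside the prediction limits rather than being set aside.

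Third, a reader might infer that agreement is bound to look too tight. Under the stated assumptions, about 37% of studies would have limits covering at least 95%, so only a tendency can be claimed.

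Fourth, a reader might infer that the plot is the plan's only evidence on agreement. Section 1 also has a radiologist and a burn surgeon compare the images directly for concordance.

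Finally, this is a pilot that admits low power and sets no agreement margin, so no stated decision turns on the width. That lowers the weight of the point but does not answer it: the admission concerns significance, whereas limits of agreement are an estimate, and nothing in the documents addresses their coverage or precision.

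**Conclusion.** The concern holds as a gap in specification with a predictable consequence. If the undefined limits are drawn by convention at ±1.96 SD, they would contain on average about 91% of future patients' differences, and fewer than 95% in about 63% of studies of this size, so agreement is likely to look tighter than it is. This rests on the assumed multiplier, on roughly normal differences and on reading the limits as prediction limits. In the non-normal cases tried, coverage of ±1.96 SD was 87% to 91%.

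The t-based multiplier should not be taken as a complete remedy, because it corrects average coverage only and leaves the larger imprecision of each limit unseen. Severity is minor to moderate.

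**What to change.** In the Statistical Analysis Plan of Section 4:

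1. State that the limits are mean difference ± t(n−1; 0.975) × SD × √(1 + 1/n), with n the number of usable pairs (2.37 SD at n = 10), and describe them as 95% prediction limits for a new patient.
2. Also report the conventional limits of agreement with a 95% confidence interval for each, about ±1.27 SD at n = 10.
3. List all 10 differences alongside the plot. Normality cannot be checked with 10 values, and coinciding points, such as several zero differences, can be hidden on a plot.

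The cost is a few lines of text, with no extra patients or imaging. The downside is that the reported limits become about 21% wider than ±1.96 SD.
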